## **6 Risk / Benefit Assessment**

Although cigarette smoking is associated with many diseases, we do not anticipate that any risk of smoking 1 cigarette during a study session is beyond the everyday risk to all participants who need to be smoking at least 5 cigarettes daily to be eligible for the study. The anticipated benefit of this study, in general, is to evaluate the effectiveness of graphic warning labels. Results from this study may then be used to guide FDA regulation of the images used on cigarette packs. Others will be able to potentially benefit from this study by having improved tobacco policy put into effect that will reduce the impact of cigarette smoking on the US population.

The potential benefits of this study outweigh the potential risks. There is only a minimal risk of experiencing study-related AEs or SAEs by enrolling in this trial. In addition, we will minimize any risks related to loss of privacy by maintaining strict confidentiality. Results from this trial, however, may have scientific and policy implications by providing empirical support for FDA policy on cigarette packaging regulation in tobacco products and educating smokers on the risks of smoking.

## **7 Data Management**

The CIRNA Data Management Team has developed a data management system (DMS) that will facilitate the operational facets of this study, including collection, validation and storage of participant data, tracking recruitment call attempts, participant study milestones, accrual goals, and exporting data for use in statistical analysis and data sharing. The DMS integrates Microsoft Access, REDCap and AutoData Scannable Office.

REDCap (Research Electronic Data Capture) is the primary software platform for collecting and storing questionnaire data. REDCap is a web-based application developed by Vanderbilt University to capture data for clinical research. It is HIPAA-compliant, and highly secure. REDCap ensures data integrity through range and validity checks during the data entry process.

In addition to REDCap, some data may be collected using scannable forms created in AutoData Scannable Office. Scannable Office uses Microsoft Word to create forms that are mapped to a MS Access database and processed with an imaging scanner. During the scanning process, response data is captured and written directly into the database. Microsoft Access is a relational database product and the primary software platform for project management. The MS Access databases contain VBA programming to automate report generation (e.g., accrual, enrollment, AE tracking, participant compliance, and recruitment sources), calculate study milestone dates, performing range/validity checks as users enter data, generate custom error messages to control user input, and populate information displayed on participant study materials.

### ***7.1 Data Management System Development***

The CIRNA Data Manager will work closely with the trial investigators to develop an understanding of the data collection, storage, and quality assessment needs for the trial. This includes the design and development of the trial data collection forms and REDCap surveys. The data collection forms will serve as templates for designing the data entry screens. The Data Manager will work closely with the investigators to design, develop, and test an appropriate database structure to support the requirements of the DMS and to promote data security and integrity. Electronic audit trails of changes to database contents (including REDCap) are incorporated into the design and will capture and record those changes automatically.

### ***7.2 Data Security***

Data collected in an Access database and REDCap will be stored on a secure server administered by the Penn Medicine Academic Computing Services (PMACS) organization and will be restricted to only those individuals who are authorized to work on the trial. Individual user accounts with passwords will be used to restrict access to the database. Specific privilege assignments within the database will also be employed to limit the types of functions that authorized users can perform to those functions that are appropriate for their role in the trial. Additional measures to prevent unauthorized external access to the database environment will be employed using network firewall technologies. The Data Manager will maintain the database in an appropriate manner for the retention period required by regulation. Database administration includes user account maintenance, database security, performance monitoring, and database change management. Daily backups are performed to protect data against accidental destruction or corruption.

### ***7.3 Data Processing***

The data entry screens will resemble the data collection forms as closely as possible to allow visual referencing during data entry. The data entry module will be configured for single data entry. The majority of participant data will be self-report and participants will either enter data into Qualtrics using computer, tablets or complete paper-and-pen forms during in-person visits. Some data might be collected by research staff, recorded on study-specific source documents/CRFs, and scanned in or entered directly into REDCap or MS Access. Data entry checks will be included in the entry screen designs, where appropriate, to limit the opportunity for erroneous entries due to mistyping. Such data entry checks would include value range comparisons, valid data type checks, required value checks, and/or skip pattern enforcement. Following initial telephone eligibility screening, research staff will perform subject registration.

Prior to lab session, research staff will randomize eligible participants. The randomization module will allow the research staff to randomize participants into one of the two trial arms. At the randomization attempt, the DMS will confirm milestones are accurate and that the randomization is valid. A randomization assignment will then be provided.

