### **5.4 Key Exclusion Criteria**

Participants who do not meet the inclusion criteria or present and/or self-report with the following criteria will not be eligible to participate in the study. After final eligibility is confirmed, participants who present and/or self-report with any of the following exclusions during the study period may only remain eligible after the case is reviewed by Principal Investigator and it is determined that the situation does not significantly impact the study design, data quality, and/or participant safety and welfare.

- Use of any nicotine-containing products other than cigarettes. Participants reporting isolated use of other nicotine containing products less than 5 times per month are eligible to participate.
- Not actively trying to quit smoking currently and had not made a quit attempt in the past month.
- Self-report current alcohol consumption that exceeds 25 standard drinks/week.
- Self-report current pregnancy or breast feeding.
- Any self-reported impairment - visual (colorblindness or impairments such as glass eye), physical, and/or neurological impairments preventing the proper completion of the study procedures.
- Serious or unstable medical condition.
- Lifetime history of schizophrenia, psychosis, and/or bipolar disorder.
- Current use or discontinuation of anti-psychotic medications within the last 6 months.
- Current diagnosis of active major depression. Participants who maintain a diagnosis of major depression who have not experienced any major depressive episodes in the past 6 months and are stable on antidepressant medication(s) are eligible to participate.

- Inability to provide informed consent or complete any of the study tasks as determined by the principal investigator.

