### ***5.6 Participant Recruitment***

[name] will oversee the study recruitment. Participants may be recruited from television, radio, internet advertisements, newspaper, flyers, transit posters, referrals, and/or from our database of previous participants who have agreed to be re-contacted for future studies. Interested participants will first complete an online RedCap screener or a telephone screen to assess their initial eligibility. Participants who are initially eligible will be screened against our registration database to confirm that they are not currently participating in another research study at our Center and have not previously reported a condition or circumstance that would make them ineligible for the current study. Those participants who remain initially eligible will then be invited to attend the lab session at our Center during which they will be presented with the IRB-approved Informed Consent Form and have their final eligibility confirmed.

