### 5.8 *Procedures*

The lab session will occur at the Center for Interdisciplinary Research on Nicotine Addiction (CIRNA). Participants will typically receive a session reminder 24 – 48 hours prior to their scheduled session via phone call, email, and text message (if applicable).

During the session (Duration: ~2 hours), participants will complete the following:

1. Confirm the accuracy of information (i.e., name, address, phone number, email [if applicable], date of birth, age, ethnicity, race, sex assigned at birth, gender, cigarette brand type) provided during the initial Telephone Eligibility Screen. Participants will be explicitly instructed to bring in their own preferred brand of cigarettes to verify their preferred brand. If the participant does not bring in the brand of cigarettes, they reported during the Telephone Eligibility Screen, the participant may be deemed ineligible or their session may be rescheduled to a later time/day.
2. Receive and review a research study summary for potential participants. If the participant is still interested in participating in the study, they will be presented with the complete combined Informed Consent Form per below.
3. Be presented with the combined Informed Consent Form. The Informed Consent Form will be read to the participant verbatim. All of the participant's questions will be answered. Both the questions and subsequent answers will be recorded on an "ICF/HIPAA Questions Form," which will be maintained with the original Informed Consent Form. If the participant agrees to participate in the study, the Informed Consent Form will be signed (legal name) and dated by both the participant and a qualified member of the research team. Participants will receive a signed copy of the Informed Consent Form for their records.
4. Smoke a cigarette (own brand) outdoors to standardize the time to last smoke.
5. Complete baseline questionnaire:
  - Cigarette Brand Form - While viewing the participant's cigarette pack, the research staff will record the cigarette brand information on the form as appropriate. Additionally, a photocopy of the participant's cigarette packaging will be obtained for further verification of preferred brand and flavor.
  - Demographics and Sexual Orientation
  - Smoking History
  - Nicotine Dependence (FTND)
  - Pre-test measures of smoking related beliefs, attitudes towards quitting and knowledge of tobacco harms.

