  - No CO measurements will be collected during the session to minimize the risk of COVID-19 infection.

6. Participants will then have their eye tracking session, completing a calibration task followed by exposure to their assigned graphic warning labels. Participants will then complete a recall task and a questionnaire with knowledge, risk beliefs and attitude measurement.
7. After viewing labels from their assigned group, each participant will perform a recognition and ranking task for all 11 labels proposed for cigarette packs by the FDA.
8. Participants will be provided compensation for their participation.

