### ***8.3 Monitoring Activities***

#### ***8.3.1 Initial Assessment (Lab Session) Monitoring***

The study staff will conduct a manual quality assurance review of a participant's telephone screen documentation to confirm the participant's initial eligibility prior to their session. Further, eligibility data will be closely reviewed in real-time by the research staff.

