### 9.1 *Informed Consent and HIPAA*

Prospective participants will be informed about the study and interviewed for eligibility on the phone with a trained research assistant. After a participant is deemed eligible, the lab session will be scheduled within a month of completing the phone screen. A trained staff member will obtain informed consent using an Informed Consent Form approved by the Penn IRB. The consent process will take place prior to the initiation of any study procedures and will take place in English. The consent process will occur in person at the CIRNA and will involve a discussion of the study requirements and procedures. The Informed Consent Form will be read verbatim to participants. Participants will have an opportunity to ask any questions and/or express concerns that may have. Participants will receive a copy of the Informed Consent Form for their records. If the participant agrees to participate in the study, the Informed Consent Form must be signed (legal name) and dated by both the participant and the investigator-designated staff member obtaining the consent.

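### Section 7.3 randomizes before the lab session, so consent, final eligibility and baseline all follow assignment, and the plan does not reconcile this order with its other sections

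*Combined protocol and SAP*

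**What the plan says.** Section 7.3 moves from telephone screening to registration and then to allocation: "Prior to lab session, research staff will randomize eligible participants". The data management system (DMS) checks its milestones, and "A randomization assignment will then be provided". The recipient is not named and the milestones are not listed.

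The other sections place the following steps at or after arrival:

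- Section 8.3.1: staff review the screening documents "to confirm the participant's initial eligibility prior to their session". Only initial eligibility is established before the visit.
- Section 5.6: at the visit, people are "presented with the IRB-approved Informed Consent Form and have their final eligibility confirmed".
- Section 5.8: the brand check is step 1, consent step 3, the baseline questionnaire step 5, and the eye-tracking task step 6. No numbered step is randomization. If the reported brand is not brought, "the participant may be deemed ineligible or their session may be rescheduled to a later time/day".
- Section 5.4: one exclusion is "Inability to provide informed consent or complete any of the study tasks as determined by the principal investigator". The opening of that section also lets the Principal Investigator decide, after final eligibility, whether someone who shows an exclusion may stay in.
- Section 9.1: "The consent process will take place prior to the initiation of any study procedures". The session may fall up to a month after the phone screen.

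The target of 70 is attached to different events: people randomized (Section 1), people randomized and completing (Section 4.2), and people signing consent, given as approximately 70 (Section 5.2). Section 5.10 names tests and models but no analysis population.

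**The concern.** Assigning an arm before consent and final eligibility has two consequences.

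First, anyone who does not attend, declines, arrives without the required pack or proves ineligible at the visit has already been randomized and will have no outcome. Randomized and analysed numbers then differ for a reason that later allocation would remove.

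Second, some decisions at the visit involve judgement: whether a brand mismatch leads to exclusion or rescheduling, and whether a person can complete the tasks. If whoever decides can see the arm, the decision could depend on it, and the baseline knowledge questionnaire could be administered with the arm known. In a parallel comparison of about 35 per arm (assuming equal allocation), a few selective exclusions could matter.

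**Working it through.** **1. Order of events.**

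| Event | When | Source |
|---|---|---|
| Screen, registration | Before the visit | 5.7, 7.3 |
| Randomization, assignment provided | Before the visit | 7.3 |
| Brand and pack check | Visit, step 1 | 5.8 |
| Consent | Visit, step 3 | 5.6, 5.8, 9.1 |
| Final eligibility | Visit, no numbered step | 5.6, 8.4 |
| Baseline questionnaire | Visit, step 5 | 5.8 |
| First use of the arm | Visit, step 6 | 5.8 |

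Could the lab session in Section 7.3 mean only the eye-tracking part? Sections 5.6, 5.8 and 9.1 use the term for the whole visit, and Section 7.3 puts allocation directly after screening and registration. That reading does not hold. So the eligible participants of Section 7.3 can only be initially eligible, and the DMS milestones checked at that point cannot include consent or final eligibility.

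The arm is first used in step 6, which consists of "completing a calibration task followed by exposure to their assigned graphic warning labels". Nothing in the documents appears to need it sooner.

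**2. The three meanings of 70.** The counts in Sections 1, 4.2 and 5.2 agree only if nobody is lost between assignment and consent, or between assignment and completion. With a loss fraction L before confirmed eligibility, ending with 70 means randomizing 70/(1 − L):

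- L = 10%: 70/0.90 = 77.8, so 78.
- L = 20%: 70/0.80 = 87.5, so 88.

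**3. Precision, as an illustration.** The figure of 70 cannot be reproduced: the plan rests it on earlier eye-tracking work and gives no alpha, power, effect size or standard deviation. The following are assumptions: 1:1 allocation, 10% or 20% loss, no replacement, and the unpaired t-test named in Section 5.10 at two-sided 5%.

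The half-width of the 95% confidence interval, in standard deviation units, is t(0.975, n1 + n2 − 2) × √(1/n1 + 1/n2).

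| Loss | Analysed | Per arm | Half-width | Ratio to no loss | Detectable d, 80% power |
|---|---|---|---|---|---|
| 0% | 70 | 35/35 | 0.477 | 1 | 0.68 |
| 10% | 63 | 31/32 | 0.504 | 0.504/0.477 = 1.06 | 0.72 |
| 20% | 56 | 28/28 | 0.536 | 0.536/0.477 = 1.12 | 0.76 |

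The width ratios need no assumption about power or effect size. The figures apply to continuous between-arm outcomes only; the image-versus-text comparisons of Aim 1 are not between arms. If losses are replaced until 70 are analysed, every ratio is 1.

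**The case against.** A reader might infer that Section 7.3 flatly contradicts Sections 5.6, 5.8 and 9.1. That goes too far. Sections 5.6 and 5.8 give no time for randomization, and silence is not contradiction. Section 9.1 conflicts only if randomization is a study procedure, and the documents use that term loosely: the pre-consent eligibility screen sits under a Study Procedures heading, while randomization sits under Data Management. Screening, assigning, consenting and then exposing is a workable sequence, though a poorer one. This part of the objection stands, and the point is therefore that the order is unreconciled.

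A reader might also infer that session staff know the arm and that exclusions are biased. The documents do not show this. Section 7.3 names no recipient of the assignment, Section 7.2 describes database privileges limited by role, and Section 8.2 refers to study-specific procedures that are not included. Equally, role-based privileges do not establish concealment, and no section says the arm is withheld from those running the visit. Nothing says that participants learn their arm before seeing the labels, so no-shows and refusals are probably unrelated to it.

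A third tempting inference is that the trial will lose precision. The documents lean towards replacement: Section 5.2 plans 5 to 7 recruits a month (60 to 84 over the one year in Section 4.2) so that enough are randomized to complete data collection. Reminders and the pre-session review may also limit losses. This stands, and it makes the width ratios illustrative only.

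Finally, the missing analysis population matters little for no-shows and refusers, who have no data to analyse. It matters more for people who consent and see the labels but fail calibration or yield unusable recordings.

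**Conclusion.** The point holds, and should be fixed, as a matter of timing. Section 7.3 states a rule, not a gap. Following it produces avoidable losses after randomization and allows discretionary eligibility decisions after assignment. That much rests on the text alone and is firm.

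The size of the effect is not known. Bias is possible, not shown, and cannot be estimated from the documents. The cost in precision runs from none (losses replaced) to an interval about 1.06 or 1.12 times as wide (10% or 20% of 70 lost without replacement, equal allocation). The certain effect is on accounting: the number randomized, the number consenting and the number with outcomes can differ, and no rule says which is 70 or who is analysed.

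**What to change.** 1. **Section 7.3.** Replace the timing sentence with, for example: *The DMS randomizes each participant during the lab session, once signed consent, confirmed final eligibility and a completed baseline questionnaire are recorded as required milestones, and before label exposure. The assignment is not released earlier.*
2. **Section 5.8.** Add randomization as a step between steps 5 and 6, and say at which step final eligibility is recorded as confirmed.
3. **Sections 4.2 and 5.2.** State, in line with Section 1, that 70 counts participants randomized at that point, and that the number consenting may be somewhat higher.
4. **Section 5.10.** State that all randomized participants with the relevant outcome are analysed in their assigned arm, and that those without usable eye-tracking data are reported by arm. Calibration comes after the new randomization point, so some such losses will remain.
5. **Section 5.4.** Reconcile this with the Principal Investigator's review after final eligibility, so that it is clear whether someone reviewed after randomization stays in the analysis.

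The cost is protocol wording, a DMS milestone setting and one extra staff step during the visit. The DMS already checks milestones at randomization.

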## **8 Data and Safety Monitoring**

### ***8.1 Research Roles***

During the study, data and safety monitoring will be performed on an ongoing basis by the Principal Investigator, research staff, and the Penn IRB. The research staff are responsible for collecting and recording all data. Research staff will meet and communicate on a regular basis to reconcile data queries and safety concerns.

### ***8.2 Staff Training***

Staff training will consist of an initial explanation and review of the protocol, combined Informed Consent Form, source documents/REDCap/Qualtrics surveys, sample collection protocols, data management system, AE collection and reporting, and all study-specific SOPs, which will be maintained in an accessible electronic manual of procedures. In addition, during a standardized training period, the duties of each staff member will be clearly outlined, and all applicable regulations will be reviewed by senior staff and the Principal Investigator. All personnel working on this project will complete required training in the protection of human participants and the protection of PHI (i.e., HIPAA) before interacting with study data or research participants. All human participant and privacy protections certifications will be maintained in the regulatory binder.

### ***8.3 Monitoring Activities***

#### ***8.3.1 Initial Assessment (Lab Session) Monitoring***

The study staff will conduct a manual quality assurance review of a participant's telephone screen documentation to confirm the participant's initial eligibility prior to their session. Further, eligibility data will be closely reviewed in real-time by the research staff.

